4.2.4 Post-diagnosis Assessment Period

Patients diagnosed with IPF or non-IPF ILD at Visit 2 will remain and be followed in the study up to the start of drug treatment (within 6 months) or a maximum of 6 months if no drug treatment is prescribed.

“Start of drug treatment” is defined as the date the treatment is planned to commence. This includes the event of a patient receiving IPF or ILD drug treatment from a physician other than the investigator.

The length of the post-diagnosis period is thus defined as:

Post-diagnosis period = date of start of drug treatment – date of initial diagnosis or
= date of end of study visit – date of initial diagnosis

whichever comes first, where diagnosis date is taken from the IPF/ILD diagnosis eCRF page. In addition, any data point collected after initiation of treatment until EOS visit will be excluded from any analysis.

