2.2 OUTCOME MEASURES

By use of different outcome measures, a primary and multiple secondary and exploratory objectives will be investigated.

The primary objective of the study is to characterize the disease behavior of IPF during the peri-diagnostic period, where the peri-diagnostic period covers:

- the pre-diagnosis period (from inclusion into the study to diagnosis; for a maximum of 12 months).
- the post-diagnosis period (from the diagnosis to the start of drug treatment within 6 months or a maximum of 6 months after diagnosis if no treatment is started).

The investigation of the primary objective is based on Forced Vital Capacity (FVC) measurements in mL by daily home spirometry.

F. Hoffmann-La Roche Ltd
Statistical Analysis Plan MA39297, Final Version 2.0

Secondary objectives of the trial are:

- to characterize the disease behavior of non-IPF ILD during the peri-diagnostic period. This will be based on the investigation of FVC measurements in mL by daily home spirometry.
- to further characterize the disease behavior of IPF and non-IPF ILD in the peri-diagnostic period using a multidimensional approach. Hereby, a set of outcome measures will be used, which will be described in detail in the following sections.

Exploratory objectives of the trial are:

- Characterization of different subgroups
- Evaluation of the differences in FVC values at beginning of treatment, depending on reimbursement restrictions
- Evaluation of the collaboration platform
- Evaluation of the digital solution set up for the patients

Please note that the exploratory objective to evaluate the differences in FVC values at the beginning of treatment, depending on reimbursement restrictions as described in the CTP may be omitted in case that no countries with reimbursement restrictions will actually be taking part in the trial.

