2.2.1 Primary Outcome Measures

Throughout the study, patients should perform a spirometry measurement of FVC [mL] at approximately the same time each day. For this purpose, study participants will be provided with a portable handheld spirometer and a tablet computer. Each spirometer will be factory calibrated.

The primary outcome measure is pulmonary function by use of FVC measurements in mL by daily home spirometry.

Note that for every FVC measurement the quality of the manoeuvre is monitored and documented according to acceptability criteria shown in the flow chart of Appendix [3](#). Depending on different characteristics of the blow, quality criteria will be provided to the patient and documented with the measurement (e.g. “blow out faster”, “blow out longer”).

Table 1 shows which of the quality criteria are considered acceptable and not acceptable manoeuvres.

Based on the Steering Committee (SC) feedback and in order to exclude the potential learning curve of each patient, the first 7 days of measurements per patient will be

removed from the analyses. All measurements will be taken into account for the analyses in case we have more than 1 per day.

Table 1 Quality criteria for FVC measurements

Not acceptable manoeuvre	Acceptable manoeuvre

 • Blow out faster • Blow out longer • Abrupt end 	
 • Don't start too early • Avoid coughing • Good blow

For analysis purpose only non-test acceptable manoeuvres flagged as 'Good blow' will be considered. In addition, any data point collected by the device before enrollment visit and after EOS visit, respectively, will be excluded from the analysis. In case a patient received treatment before EOS visit all data after treatment start date (inclusive site spirometry etc.) will be excluded from analysis as well. In order to consider only data points that are clinically meaningful FVC values outside a range from 400 ml to 6000 ml will also be excluded from analysis.

The corresponding primary endpoint used for the investigation of disease behavior of IPF is defined as the time-adjusted semi-annual FVC decline in patients with IPF during the peri-diagnosis period. Please refer to Section [4.5.1](#) for a detailed description of statistical analysis which is used for the computation of the primary endpoint.

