4.4.3.4 IPF/ILD diagnosis

A listing and a frequency table will be provided for IPF and non-IPF ILD patients displaying details of the diagnosis (e.g. types of ILD, assessments used for diagnosis). In addition, information from working diagnosis for non-diagnosed patients will be tabulated and listed. Additionally, a Kaplan-Meier analysis is performed with respect to the time from enrollment to diagnosis, the time from enrollment to start of treatment, and time from diagnosis to start of treatment (for IPF and non-IPF ILD patients), presenting summary tables and corresponding KM plots separately by cohort. Thereby, the following rules for censoring will be applied:

- Time from enrollment to diagnosis (in weeks):

F. Hoffmann-La Roche Ltd
Statistical Analysis Plan MA39297, Final Version 2.0

Only diagnosed patients will be analyzed separately by cohort. For that reason, there will be no censoring observations.

- Time from enrollment to start of treatment (in weeks):

If a patient was diagnosed and did not start IPF/ILD treatment during the post-diagnosis period or is lost to follow-up, the patient will be censored at the time of the end of study visit, or at the last available visit during the post-diagnosis period. Frequencies of patients with events and without events, i.e. that treatment was initiated or not, will be presented together with the KM estimates.

- Time from diagnosis to start of treatment (in weeks):

If a patient was diagnosed and did not start IPF/ILD treatment during the post-diagnosis period or is lost to follow-up, the patient will be censored at the time of the end of study visit, or at the last available visit during the post-diagnosis period. Frequencies of patients with events and without events, i.e. that treatment was initiated or not, will be presented together with the KM estimates.

The duration of pre- and post-diagnosis periods is analyzed by use of a summary table.

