From inclusion into the study, patients will be followed for a maximum of 12 months in the pre-diagnosis assessment period. Following thorough assessments and diagnoses, three groups of patients will be identified:

- Patients diagnosed with IPF.
- Patients diagnosed with an ILD other than IPF.
- Patients diagnosed with a condition that is not an ILD.

For individual patients, the end of the study will be as follows:

- Should no diagnosis be made 12 months after inclusion into the study, the patient will leave the study.
- Patients diagnosed with a non-ILD condition will leave the study on the date of diagnosis.
- Patients diagnosed with IPF or non-IPF ILD will remain and be followed in the study up to the start of drug treatment (within six months) or a maximum of six months if no drug treatment is prescribed.

“Start of drug treatment” is defined as the date when treatment commences. This includes the event of a patient receiving IPF or ILD drug treatment from a physician other than the investigator.

Accordingly, the total length of the study is variable for each patient, with a maximum of 18 months.

Site visits will be conducted at a minimum at baseline, diagnosis, and end-of-study for each individual patient. During each study period (pre- and post-diagnostic period), every patient should have at least one site visit, scheduled at the discretion of the Investigator. During these visits, any relevant information such as treatments given and results from HRCTs, radiographs, DLCO, lung biopsies etc. will be collected, as available.

The 6MWT and FVC measurements will be assessed on-site as per the Schedule of Activities (Appendix 1).

The study will be conducted under the leadership of a Steering Committee.

In the absence of the use of any therapeutic agent, an Independent Review Committee IRC/IRF or a Data Safety Monitoring Board (DSMB)/ Data Monitoring Committee (DMC) will not be needed in this study.

Patient study-specific assessments / study kit

Upon study enrollment, each patient will receive a study kit with a unique identifier containing the following:

- Hand-held spirometer (Device to measure daily FVC at home).
- Accelerometer (Device to continuously measure daily activities, such as steps per day, physical activity level).

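### SAP 4.2.4 sets the start of drug treatment at a planned date while the synopsis in the same SAP uses an actual date; separately, the accelerometry deletion rule in 2.2.2.2 is worded in reverse

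*SAP*

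**What the plan says.** **Treatment start.** Two definitions of the same term stand in the SAP. Section 4.2.4 says that it "is defined as the date the treatment is planned to commence". The synopsis, which Section 2.1 brings in as Appendix 1, says that it "is defined as the date when treatment commences".

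Section 4.2.4 derives the post-diagnosis length as treatment start minus initial diagnosis, or EOS visit minus initial diagnosis, whichever is earlier. The same section then says that "any data point collected after initiation of treatment until EOS visit will be excluded from any analysis". The term also bounds follow-up in Sections 2.2 and 4.2.5.

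Other rules use wording closer to an actual start. Section 2.2.1 states: "In case a patient received treatment before EOS visit all data after treatment start date (inclusive site spirometry etc.) will be excluded from analysis". Section 4.4.3.4 describes the Kaplan-Meier event with the words "i.e. that treatment was initiated or not".

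On outputs, Section 4.4.3.4 states: "The duration of pre- and post-diagnosis periods is analyzed by use of a summary table". Section 4.5.5 repeats the durations for several subgroups. Section 4.4.1 counts patients with and without a treatment start.

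**Accelerometry.** Section 2.2.2.2 removes the first 7 days of measurements and limits steps per day to 200 to 20000. It also has a sentence that deletes data over a window opening before the enrollment visit and closing at the earlier of treatment start or EOS visit. For spirometry, Section 2.2.1 instead removes what lies before enrollment, after EOS and after treatment start.

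**The concern.** A planned date and an actual date are different variables. If they differ for a patient, two programmers who both follow the SAP can derive different post-diagnosis lengths. One could also use the planned date for the period length and the actual date for data exclusion, because Section 4.2.4 points to each in turn. The duration summary and its subgroup repeats are directly exposed. The Kaplan-Meier analyses of time to treatment and the disposition counts may be exposed too, but their sections do not say which date they take.

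The accelerometry sentence is a different matter. It is an operative data rule that, taken at its word, removes what should be kept. It governs the steps-per-day data used in the correlation with the 6-minute walk test (Section 4.5.2) and in the definition of progressing patients (Section 4.4.3.3).

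**Working it through.** The plan gives no figure on this point to reproduce. The check sets the texts side by side and then applies the SAP's own length formula.

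**Step 1: which date each place uses.**

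| Place in SAP | Wording points to |
|---|---|
| 4.2.4, definition | planned date |
| 4.2.4, length formula | the defined term, so planned date |
| 4.2.4, data exclusion | initiation, most naturally actual |
| Appendix 1, definition | actual date |
| 2.2.1, spirometry exclusion | treatment received, most naturally actual |
| 4.4.3.4, Kaplan-Meier event | treatment initiated, most naturally actual |
| 2.2 and 4.2.5, end of follow-up | the defined term, no date of their own |

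Only 4.2.4 and Appendix 1 are definitions. The other rows show how the term is used.

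**Step 2: when the length becomes ambiguous.** Count days from diagnosis (day 0):

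length = min(treatment start, EOS)

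The planned and actual versions differ only if the two dates differ and the earlier one falls before EOS.

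**Step 3: examples.** All dates are assumptions, as the documents give none. EOS is day 60 in A to C and day 183 in D.

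| Case | Planned | Actual | Length, planned | Length, actual |
|---|---|---|---|---|
| A | 30 | 58 | min(30, 60) = 30 | min(58, 60) = 58 |
| B | 50 | 70 | min(50, 60) = 50 | min(70, 60) = 60 |
| C | 65 | 70 | min(65, 60) = 60 | min(70, 60) = 60 |
| D | 30 | never | min(30, 183) = 30 | 183 |

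If the Kaplan-Meier event follows the same date, the time from diagnosis to treatment becomes:

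- A: event at 30/7 = 4.3 weeks, or at 58/7 = 8.3 weeks.
- B: event at 50/7 = 7.1 weeks, or censored at 60/7 = 8.6 weeks.
- C: censored at 8.6 weeks either way.

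**Step 4: scale.** Take the maximum post-diagnosis period as 183 days, the SAP's own half-year in Section 4.5.1. If both dates precede EOS, an assumed gap of 7, 14 or 28 days is 7/183 = 3.8%, 14/183 = 7.7% or 28/183 = 15.3% of that period.

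**Step 5: the primary slope.** Data after initiation are already excluded by Section 4.2.4. The most that could be lost is untreated readings between a planned date and a later actual date, if the start date in Section 2.2.1 is read as planned.

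**Step 6: accelerometry.** The window named in Section 2.2.2.2 covers the whole untreated time on study. Deleting it would remove the home-measurement baseline of Section 4.2.2, which is averaged over the 7 days that follow the first 7, and every steps-per-day value up to treatment start or EOS. The 7-day removal and the 200 to 20000 range would then have no on-study pre-treatment data to act on. The sentence itself deletes nothing after treatment start or EOS. It is therefore the reverse of the spirometry rule in Section 2.2.1.

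**The case against.** **Only one competing definition exists.** References elsewhere to a treatment start date, or to treatment being initiated, can be read as shorthand for the term in 4.2.4. Section 2.2 ends with "a maximum of 6 months after diagnosis if no treatment is started", but the same item closes the period at the start of drug treatment, so it is not independent evidence for an actual date. This stands in part: the contradiction proper is between 4.2.4 and Appendix 1. Even so, 4.2.4 uses planned and initiated wording side by side without linking them.

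**The planned date may be deliberate.** Section 2.2.4 has patients stop the study before they start treatment, so an actual start will often fall after EOS and a planned date may be all that is on file. That is plausible, but the SAP does not say so. It also means that where both dates fall on or after EOS, as in case C, nothing changes. Sections 2.2.1 and 4.2.4 nevertheless provide for patients treated before EOS.

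**Censoring of later starts.** A reader might infer that the SAP leaves open what happens to a start after EOS. It does not. Section 4.4.3.4 says of a diagnosed patient who "did not start IPF/ILD treatment during the post-diagnosis period or is lost to follow-up, the patient will be censored" that this is done at the EOS visit or last available visit, and 4.2.4 closes the period at EOS at the latest. Once the date is fixed, a start dated after EOS is censored, so no further rule is needed.

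**The accelerometry sentence would never be programmed as written.** Probably so: its intent can be inferred from Section 2.2.1 and from the other two rules in the same section. That limits the harm, but the rule is still wrong as it stands.

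**Conclusion.** Both parts hold, at minor severity. The SAP defines one term in two ways, and the synopsis is a current appendix rather than an amendment log, so the conflict is live. The post-diagnosis length is ambiguous for patients whose planned and actual dates differ with the earlier one before EOS. The documents do not say how many such patients there are or how far apart the dates lie. The 3.8% to 15.3% range rests wholly on assumed gaps.

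A reader might infer that the primary result is at risk. The documents do not support that: post-initiation data are excluded, any loss is limited to some untreated readings, and the outputs chiefly affected are descriptive. Nor do they show that accelerometry data will in fact be lost; what they show is a sentence that reverses its evident purpose.

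**What to change.** 1. Reconcile Section 4.2.4 and the synopsis to one analysis date for the start of drug treatment. Use it consistently for period length (4.2.4), data exclusion (2.2.1 and 4.2.4), disposition (4.4.1) and Kaplan-Meier events (4.4.3.4). Which date applies is for the sponsor to settle; this concerns the analysis date only.
2. Reword Section 2.2.2.2 so that accelerometer data are deleted if collected before the enrollment visit, or after the earlier of treatment start or EOS visit.

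The cost is one reconciled definition and one reworded sentence, with no new data collection requested. Both changes should be made before final programming.

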2.2.4 Safety Outcome Measures

This study has no protocol mandated investigational medicinal product (IMP) or treatment requirements. Patients will stop the study prior to starting any drug treatment for IPF/ILD.

Any occurrence of non-elective hospitalization, Investigator-reported acute exacerbations, deaths, and events related to study assessments will be collected in the eCRF only.

Any untoward occurrences thought to be due to, or associated with, a commercial medicinal product used during the course of a patient’s standard medical treatment will not be reported in the eCRFs, but should be reported to the respective Market Authorization Holder or local Health Authority according to local regulatory requirements.

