4.2 TRIAL PERIODS, OBSERVATION AND ANALYSIS TIMES

The study consists of the peri-diagnosis period (from enrollment until end of study visit), which is divided into a pre- and post-diagnosis period (please refer to Sections [4.2.3](#) and [4.2.4](#) for the definition of these periods). Site visits will be conducted at a minimum at baseline, diagnosis, and end-of-study for each individual patient. During each study period, every patient should have at least one site visit, scheduled at the discretion of the investigator.

All patients will be managed at the discretion of the Investigator taking into account local clinical practice guidelines and standards of care as well as available clinical evidence for patients with suspected IPF/ILD or diagnosed with IPF/ILD.

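### Section 4.2.4 removes everything collected after treatment start from all analyses, which contradicts the window the safety section sets for study-assessment events

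*SAP*

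**What the plan says.** The exclusion appears twice. Section 4.2.4, which is part of the general definitions of trial periods, says that "any data point collected after initiation of treatment until EOS visit will be excluded from any analysis". Section 2.2.1, on the home FVC measurements, says that for a patient treated before the EOS visit "all data after treatment start date (inclusive site spirometry etc.) will be excluded from analysis as well". Neither place mentions safety, and Section 4.7 contains no exception.

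On periods, Section 2.2 lets the post-diagnosis period run "from the diagnosis to the start of drug treatment within 6 months", or to six months after diagnosis if no treatment starts. Section 4.2.4 likewise ends it at treatment start or the EOS visit, whichever is earlier. Section 4.2 takes the whole period further: "The study consists of the peri-diagnosis period (from enrollment until end of study visit".

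On safety, Section 2.2.4 says: "Any occurrence of non-elective hospitalization, Investigator-reported acute exacerbations, deaths, and events related to study assessments will be collected in the eCRF only". The same section states the design intent: "Patients will stop the study prior to starting any drug treatment for IPF/ILD". Section 4.7.1 counts hospitalisations, acute exacerbations and deaths by pre- and post-diagnosis period. It tabulates study-assessment events over the peri-diagnosis period, using an allocation rule of its own that does not refer to treatment start.

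The cut-off date has two definitions. In Section 4.2.4 start of drug treatment "is defined as the date the treatment is planned to commence"; in the synopsis (Appendix 1) it "is defined as the date when treatment commences".

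**The concern.** Stopping FVC and step data at treatment start is sensible, because drug treatment would change the untreated course that the study sets out to describe. That reasoning does not carry over to harm from the study's own procedures. Site spirometry and, where feasible, the 6MWT are scheduled at the EOS visit. An adverse event from either is a harm of taking part whether or not the patient has begun treatment. A programmer who applies Section 4.2.4 as written would remove such an event from the tables, while one who applies Section 4.7.1 as written would keep it. Two correct readings of the same plan would give different harm tables, and the incidence of these events is one of the endpoints in Table 3.

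**Working it through.** No figure in the SAP bears on this point, so the check sets the provisions side by side.

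**1. Can data exist between treatment start and the EOS visit?** The design intent is that patients leave before treatment. But Section 2.2.1 provides for treatment before the EOS visit, Section 4.2.4 provides for the gap up to that visit, and Section 4.2.4 also covers treatment begun by a physician other than the investigator. The SAP itself anticipates the gap.

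**2. What happens to each event type in that gap?**

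| Event type | Window in 4.7.1 | Where that window ends | Effect of the 4.2.4 exclusion |
|---|---|---|---|
| Hospitalisation, exacerbation, death | Pre- and post-diagnosis periods | Treatment start or EOS, whichever is first (4.2.4) | None further by onset: already outside |
| Study-assessment event | Peri-diagnosis period | EOS visit (4.2); no treatment cut in the 4.7.1 rule | Removes what 4.7.1 would keep |

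The contradiction is therefore confined to the second row. It also gives the peri-diagnosis period two possible ends: treatment start if built from the sub-periods in Sections 2.2 and 4.2.4, and the EOS visit in Section 4.2.

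**3. What does the rule key on?** It refers to when a data point is collected, not to when an event began. Appendix 2 schedules the recording of all four event types at visits. An event that began before treatment but was first recorded at a later EOS visit could be excluded on a literal reading. This wording is also the one route by which a hospitalisation or exacerbation inside the untreated window could be lost.

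**4. Where does the cut fall?** If planned and actual treatment dates differ, the two definitions place an event between them on opposite sides of the cut. The passages must be reconciled before any safety window can be programmed.

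**5. Size.** The documents give neither the interval from treatment start to EOS nor any event count, so the loss cannot be derived. One consequence can be illustrated. Section 4.7.1 adds a Kaplan-Meier analysis when incidence exceeds 15%. Assume incidence is counted as patients with an event, within a cohort of the planned size (72 IPF, 90 non-IPF ILD; Section 2.3):

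- IPF: 0.15 × 72 = 10.8, so 11 patients are needed (11/72 = 15.3%). With one removed, 10/72 = 13.9%.
- Non-IPF ILD: 0.15 × 90 = 13.5, so 14 are needed (14/90 = 15.6%). With one removed, 13/90 = 14.4%.

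At the threshold, one removed patient decides whether the analysis is run. This shows sensitivity only and does not estimate the loss.

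**The case against.** The strongest reply is that the exclusion was never meant for events. The term *data point* is used elsewhere for device readings (Sections 2.2.1 and 2.2.2.2) and for values entering the FVC regression (Appendix 1). The parallel rule in Section 2.2.1 names only site spirometry as an example. Section 4.7.1 has its own allocation rule and, being more specific, could be taken to govern. This is a plausible account of the intention, but the text does not say so, and Section 4.2.4 explicitly reaches every analysis.

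Three stronger readings are tempting and are not supported:

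- A reader might infer that the incidences of death, hospitalisation and exacerbation are biased low. That would hold only if the target were incidence through the EOS visit. The SAP's window for them ends at treatment start, and an untreated-period incidence is a legitimate target.
- A reader might infer that the events are lost altogether. Section 2.2.4 has them collected. Section 4.7.1 promises a listing of all study-assessment events and listings of the other three types. The likelier outcome is that tables and listings disagree.
- A reader might size the loss as the EOS visit's share of site visits, one in three (33%) from the minimum of baseline, diagnosis and EOS. But Section 4.2 and Appendix 2 also call for at least one visit in each assessment period, which makes five visits and 1/5 = 20%. Neither share measures events lost, and daily home spirometry is a study assessment too.

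It also stands that the study has no investigational product, is descriptive, and that its primary endpoint is not affected.

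**Conclusion.** The point holds for events related to study assessments. Section 4.2.4, read literally, removes from the harm tables events that Sections 4.2 and 4.7.1 would count, including those arising from procedures at an EOS visit after treatment start. Because it refers to collection rather than onset, it can also catch earlier events that are recorded late. For deaths, hospitalisations and exacerbations with onset after treatment start, the tables omit them by design. That is a gap in what is shown and not a bias in the untreated-period incidence.

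The size is unknown. It depends on how many patients attend an EOS visit after starting treatment and on the interval between the two, and the documents give neither. The conclusion assumes only that such patients occur, as the SAP anticipates, and that Section 4.2.4 would be programmed as written. It is worth correcting because the rule contradicts the safety section, affects a named endpoint and is cheap to repair.

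**What to change.** - In Sections 4.2.4 and 2.2.1, limit the exclusion to efficacy and functional measurements: home and site FVC, steps, 6MWT and PRO.
- In Section 4.7.1, state that study-assessment events are tabulated by onset date, from enrollment through the EOS visit.
- Keep the untreated-period counts of deaths, hospitalisations and exacerbations as the main result. Show those with onset between treatment start and the EOS visit in a separate flagged row.
- Reconcile the definitions of start of drug treatment in Section 4.2.4 and Appendix 1, since that date sets the cut-off.

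The cost is a few sentences and one row or flag in the safety tables; the events are already collected in the eCRF. The drawback is that follow-up after treatment start depends on when each EOS visit happens to take place, so the flagged row should give counts only, without rates or comparisons.
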